7.4 Follow-Up and Record of Events (Form D)

- The patient should be followed-up until death.
- The dates of diagnosis of in-field, out-of-field (intra-hepatic), and distant failure should be recorded.
 - In-field failure: defined as recurrence within the high-dose region (80% iso-dose volume), demonstrated by new enhancement or mRECIST progressive disease.
 - Out-field (intra-hepatic): defined as new or mRECIST progressive disease within liver parenchyma, but outside the SBRT treated volume
 - Distant failure: defined as new disease outside liver parenchyma
- The incidence of late toxicities \geq grade 3 by Common Toxicity Criteria for Adverse Events version 4.0 (CTCAE-v4) should be recorded.
- All causes of death (if occur) will be recorded. Deaths due to unknown cause are counted as deaths due to HCC if disease is still present at last assessment.

7.5 Criteria for Removal From Protocol Treatment

- Disease progression
- Inter-current disease that would affect assessments of clinical status to a significant degree, require discontinuation of drug, or both
- Unacceptable toxicity
- The patient may withdraw from treatment at any time for any reason. The reason should be recorded. Follow-up will be continued for all consenting patients per standard clinical procedures, including regular follow-up visits, clinical and laboratory assessments for up to 5 years

- Avelumab treatment for maximum of 2 years

7.6 Exploratory Biomarkers

- **Blood Borne Immune Panel Exploratory Analysis**

Peripheral blood monocytic cells (PBMC) will be collected at baseline, then every 4 weeks after initiation of treatment for 20 weeks.

Procedure: after collection of patients' blood, the sample will be centrifuged for 15 min at 3000 rpm. After removal of the plasma, PBMC will be isolated either by Ficoll-paque or red cell lysis buffer. The isolated PBMC will be washed twice with PBS for immediate analysis or frozen for further investigation. For the phenotyping of the immune cells, PBMC will be stained with different antibodies and examined by flow cytometry. The identification of CD8+ and CD4+ T cells are defined as CD8+ CCR7+ CD45RA+ and CD4+ CCR7+ CD45RA+, respectively. For the T-reg cell, we define as positive for CD4 and Foxp3. We will also examine the expression of Ki-67 and TIM-3 in the T-cells to demonstrate the possible cell proliferation and functions. We will also examine the expression of PD-1 and PD-L1 expression on each subset of cell to correlate the pathological response and clinical outcome.

- **Tumor samples (immune-related markers in surgical specimens)**

The expression and spatial distribution of immune-related or response-related markers by immunohistochemistry may also include, but may not be limited to, PD-L1, CTLA-4, CD3, CD4, CD8, CD45RO, forkhead box P3, granzyme B, OX40, PD1, cleaved caspase 3 and Ki67.

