1.3 Immune Checkpoint Inhibitors (ICI)

Immune checkpoint inhibitors (ICI) represent another breakthrough in the management of advanced HCC patients. Preclinical data have shown that HCC's tumor microenvironment is immunosuppressive; (22) the overexpression of inhibitory proteins PD-1 and CTLA-4 on the exhausted T-cells has rendered the checkpoint inhibitors a promising therapeutic option. (23)

The first published report on checkpoint inhibition in HCC is a phase II trial using the CTLA-4 inhibitory antibody tremelimumab. The trial enrolled 21 patients with hepatitis C-related cirrhosis. Among 17 evaluable patients, three (18.0%) had a partial response, and an additional 10 (58.8%) had stable disease, with a median time to progression of 6.5 months. However, nearly half (45%) of all patients experienced grade 3 or higher toxicity, primarily transaminase elevations. Typical immune-related toxicities such as rash (65%) and diarrhea (30%) were common, but no patients required corticosteroid treatment for toxicity. (24) Later, the checkmate-040 phase I/II trial was recently published, among 214 of advanced HCC patients received anti-PD1 Nivolumab 3mg/Kg every 2 weeks, the objective response rate (ORR) was 20%, the median duration of response was 9.9 months, and the toxicity profile was manageable. (25) The favorable ORR and durability of response have lead to FDA accelerated approval of Nivolumab in HCC patients who have previously been treated with Sorafenib.

There is evidence of synergistic effect from the combination of immunotherapy regimes with SBRT. Radiation could induce immunogenic cell death and convert the irradiated tumor into an in-situ vaccine to prime the immune system for the checkpoint inhibition. (26) Pre-clinical data have demonstrated that the combination of SBRT and checkpoint inhibition resulted in

better local tumor regression and abscopal (out-of-field) effect when compared with the use of either single modality treatment. (27-28) Early clinical reports in melanoma and lung cancer patients have provided further support for the efficacy and safety of this novel combination. (29-30). In the randomized phase III PACIFIC trial in stage III non-small cell lung cancer, patients were randomized to receive anti-PD-L1 Durvalumab or placebo after completion of chemo-radiation, the PFS was significantly longer in patients receiving checkpoint inhibitors (16.8 months versus 5.6 months, $p<0.0001$). (31)

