5. REGISTRATION PROCEDURE

5.1 Clinical Evaluation / Management

- Document performance status
- Documentation of liver disease etiology including cirrhosis, hepatitis history (hepatitis B and hepatitis C), alcohol, autoimmune disease, non-alcoholic steatohepatitis (NASH)
- Documentation of prior HCC therapies
- Initiation of treatment of viral hepatitis B (if untreated) prior to study therapy
- Patients with known portal hypertension or known history of varices are encouraged to have an endoscopic assessment of and appropriate treatment of varices within 6 months of study entry
- Blood tests including complete blood picture, liver function test, renal function test, free T4 and TSH, eGFR, clotting profile within 28 days prior to study entry
- Alpha-fetoprotein (AFP) within 28 days prior to study entry

- Urine or serum pregnancy test every 4 weeks while on avelumab therapy
- Free T4 and TSH must be performed at baseline and at least every 8 weeks during avelumab treatment and at end of treatment or 30 days post-treatment safety follow-up (if not performed in the previous 8 weeks)
- 20cc blood for bio-banking: Peripheral blood monocytic cells (PBMC) will be collected to analyze the peripheral T-cell response during treatment

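### The exploratory blood panel (protocol section 7.6) defines CD8+ and CD4+ T cells by the naive phenotype, so as written it would largely miss the circulating T-cell response

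*Protocol*

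**What the plan says.** Section 7.6 of the protocol describes the blood immune panel. Mononuclear cells are isolated, stained and read by flow cytometry, at baseline and then every 4 weeks for 20 weeks.

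- The conventional T-cell populations are fixed by this sentence: "The identification of CD8+ and CD4+ T cells are defined as CD8+ CCR7+ CD45RA+ and CD4+ CCR7+ CD45RA+, respectively".
- One further population is defined: "For the T-reg cell, we define as positive for CD4 and Foxp3".
- Proliferation and function markers follow: "We will also examine the expression of Ki-67 and TIM-3 in the T-cells to demonstrate the possible cell proliferation and functions".
- So do the checkpoint markers: "We will also examine the expression of PD-1 and PD-L1 expression on each subset of cell to correlate the pathological response and clinical outcome".

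Section 5.1 gives the reason for taking the blood: "to analyze the peripheral T-cell response during treatment".

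No other part of the protocol defines a total, central-memory, effector-memory or terminal effector population for the blood panel. CD3 and CD45RO are named only in the immunohistochemistry list for surgical specimens.

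**The concern.** The sentence is worded as the identity of the CD8+ and CD4+ T cells as a whole, not as one subset among several. The phenotype it gives is that of naive cells. T cells that have met antigen and differentiated leave that phenotype, and so leave the gate. Yet Ki-67, TIM-3 and PD-1 are to be read in the populations so defined, to show proliferation and function and, for PD-1, to relate to outcome.

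What is at stake is whether the exploratory result can be interpreted. If Ki-67 or PD-1 on conventional T cells stayed flat over the serial samples, the reader could not tell a true lack of response from a gate that excludes most of the cells in which a response would appear. Patients would have given repeated samples for a readout that, as defined, looks largely in the wrong place.

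**Working it through.** The plan states no figure here and there is none to reproduce. The check is one of logic: lay the written gate over the four populations that CCR7 and CD45RA separate, then compare the result with the stated purpose.

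Inputs from the protocol: the two gates, the T-reg definition and the markers (section 7.6), and the purpose of the samples (section 5.1). Input from general immunology: the conventional naming of the four quadrants.

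| CCR7 | CD45RA | Conventional name | Inside the section 7.6 gate? |
|---|---|---|---|
| + | + | Naive (with the small stem-cell-memory fraction) | Yes |
| + | − | Central memory | No |
| − | − | Effector memory | No |
| − | + | Terminal effector | No |

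Step 1. The gate keeps 1 quadrant of 4 and drops 4 − 1 = 3, for CD8+ and CD4+ alike.

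Step 2. The three dropped quadrants are the main antigen-experienced conventional populations. Stem-cell-memory cells are antigen-experienced too, but share the naive phenotype and stay in.

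Step 3. T-regs are defined by CD4 and Foxp3 with no CCR7 or CD45RA condition, so they are unaffected, and PD-1 read on each subset would include them.

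Step 4. The populations defined for the blood panel are therefore naive-phenotype CD8+ cells, naive-phenotype CD4+ cells and T-regs. Ki-67 and TIM-3 in the T cells, and PD-1 on each subset, have no other defined population to refer to.

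Step 5. Section 5.1 wants the T-cell response during treatment. For conventional T cells, the gates in step 4 are mostly made up of cells that have not yet responded to antigen. The definition and the purpose do not fit.

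The count of quadrants is not a count of cells. Turning it into a percentage lost would need the naive share of CD8+ and CD4+ cells in these patients, which the protocol does not give.

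**The case against.** The strongest reply is that this is a gate applied in analysis, not a physical loss. If the markers are stained on the same cells, the files can be re-gated. Section 7.6 allows cells to be frozen, and section 8.1 allows changes to exploratory analyses to be documented in the final report. The work is exploratory: the matching objective in section 2.2 is only to collect specimens for later correlative studies, and no endpoint, stopping rule or treatment decision uses these markers. The laboratory may also intend a broader meaning of T cells than the sentence gives. All of this stands, and it limits the harm. It does not remove the error. The protocol did not leave the gate to a laboratory manual; it fixed a definition, and nothing else in the text supplies the broader one.

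A reader might infer four stronger things, which the documents do not support.

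- That the gate contradicts the rationale in section 1.3, which speaks of "the overexpression of inhibitory proteins PD-1 and CTLA-4 on the exhausted T-cells". That sentence describes the tumor microenvironment, not circulating cells, so it does not by itself conflict with a blood gate.
- That the panel can show no response at all. T-regs and stem-cell-memory cells remain in view, and re-gating may recover the rest.
- That PD-L1 readings on treatment would be distorted because avelumab occupies the target. No detection clone is named, so this is a conjecture about an unspecified reagent.
- That the gate is what would spoil the correlation with pathological response. Only operated patients have pathology. Under the 20% alternative in section 8.2 that is 0.20 × 29 = 5.8, about 6 patients, so this correlation would be weak with any gate. Correlation with clinical outcome is not limited in this way.

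**Conclusion.** The point holds in a limited form. Section 7.6 wrongly states the definition of CD8+ and CD4+ T cells: it gives the naive phenotype and excludes conventional central-memory, effector-memory and terminal effector cells. Followed literally, Ki-67, TIM-3 and PD-1 on conventional T cells would be measured mainly in naive cells, and the panel would largely miss what section 5.1 collects the blood for.

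This rests on two assumptions: the conventional reading of CCR7 and CD45RA, which is not in dispute, and that the laboratory gates as the sentence says. If it already gates more broadly, only the text is wrong.

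The consequence is confined to the exploratory analysis and can be corrected. The primary endpoint, the two-stage design, the sample size and the error rates do not change. No numerical size is claimed beyond three of four quadrants excluded. The protocol also does not say how a flat result would be read, so a false conclusion of no immune activation is a risk and not a planned inference.

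**What to change.** Amend section 7.6 as follows.

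1. Define the parent populations as total CD3+CD8+ and total CD3+CD4+ T cells, and keep the T-reg definition.
2. Use CCR7 and CD45RA only to split each parent into naive, central-memory, effector-memory and terminal effector subsets.
3. State that Ki-67, TIM-3 and PD-1 are reported in the total and in the antigen-experienced subsets.
4. For samples already processed, re-gate the existing flow files or re-stain frozen cells where possible, and record the change in the final report as section 8.1 provides.

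The cost is a CD3 stain and slightly more flow analysis, with no extra blood or visits. Samples analysed at once and not frozen cannot be re-stained, so for those the correction is limited to what the stored files contain.

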7.7 Safety Reporting

7.7.1 Adverse Events (AE)

According to the ICH guideline for Good Clinical Practice, an adverse event is any untoward medical occurrence in a clinical investigation subject administered a pharmaceutical product, regardless of causal attribution. An adverse event can therefore be any of the following:

- Any unfavorable and unintended sign (including an abnormal laboratory finding), symptom, or disease temporally associated with the use of a medicinal product, whether or not considered related to the medicinal product
- Any new disease or exacerbation of an existing disease (a worsening in the character, frequency, or severity of a known condition)
- Recurrence of an intermittent medical condition (e.g., headache) not present at baseline
- Any deterioration in a laboratory value or other clinical test (e.g., ECG, X-ray) that is associated with symptoms or leads to a change in study treatment or concomitant treatment or discontinuation from study drug

- Adverse events that are related to a protocol-mandated intervention, including those that occur prior to assignment of study treatment (e.g., screening invasive procedures such as biopsies)

7.7.2 Serious Adverse events (SAE)

A serious adverse event is any adverse event that meets any of the following criteria:

- Is fatal (i.e., the adverse event actually causes or leads to death)
- Is life threatening (i.e., the adverse event, in the view of the Investigator(s), places the patient at immediate risk of death)
- This does not include any adverse event that, had it occurred in a more severe form or was allowed to continue, might have caused death.
- Requires or prolongs inpatient hospitalization
- Results in persistent or significant disability/incapacity (i.e., the adverse event results in substantial disruption of the patient's ability to conduct normal life functions)
- Is a congenital anomaly/birth defect in a neonate/infant born to a mother exposed to study drug
- Is a significant medical event in the Investigator(s)'s judgment (e.g., may jeopardize the patient or may require medical/surgical intervention to prevent one of the outcomes listed above)

The terms “severe” and “serious” are not synonymous. Severity refers to the intensity of an adverse event (e.g., rated as mild, moderate, or severe, or according to National Cancer Institute Common Terminology Criteria for Adverse Events [NCI CTCAE]; the event itself may be of relatively minor medical significance (such as severe headache without any further findings).

Severity and seriousness need to be independently assessed for each adverse event recorded in the clinical database.

7.7.3 Adverse Events of Special Interest (AESI)

AESIs (serious or non-serious) are a subset of Events to Monitor of scientific and medical concern specific to the Merck Drugs in this protocol for which ongoing monitoring and rapid communication by the Investigator(s) to Merck Drug Safety is required. Such an event might require further investigation in order to characterize and understand it.

Infusion related reactions including study intervention hypersensitivity reactions and immune-mediated adverse reactions (immune-related pneumonitis, immune-related colitis, immune-related hepatitis, immune-related endocrinopathies (thyroid disorders, adrenal insufficiency, new onset type I diabetes mellitus, pituitary disorders), immune-related nephritis and renal dysfunction and other immune-related AEs (myositis, myocarditis, Guillain-Barré syndrome, uveitis) have been identified as adverse events of special interest for avelumab.

Any AE that is suspicious to be a potential immune-mediated adverse reaction or infusion related reaction will be considered an AESI. AESIs do not require expedited reporting unless

they are serious. Should the AESI be serious, a SAE form should be filled instead and the reporting process for SAEs should be followed.

7.7.4 Pregnancy Reports

Female patients of childbearing potential will be instructed to immediately inform the Investigator(s) if they become pregnant during the study.

7.7.5 Assessment of Causality of Adverse Events

Investigator(s) should use their knowledge of the patient, the circumstances surrounding the event, and an evaluation of any potential alternative causes to determine whether an adverse event is considered to be related to the study drug, indicating “Yes” or “No” accordingly. The following guidance should be taken into consideration:

- Temporal relationship of event onset to the initiation of study drug
- Course of the event, with special consideration of the effects of dose reduction, discontinuation of study drug, or reintroduction of study drug (as applicable)
- Known association of the event with the study drug or with similar treatments
- Known association of the event with the disease under study
- Presence of risk factors in the patient or use of concomitant medications known to increase the occurrence of the event
- Presence of non-treatment-related factors that are known to be associated with the occurrence of the event

7.7.6 Methods of Recording Adverse Events

All AEs must be documented in the appropriate section of the CRF. An SAE report form (initial or follow up) must be completed in addition.

The following aspects must be recorded for each event in the CRF:

A description of the AE in medical terms, not as reported by the subject;

- The date of onset (start date)
- The time of onset (start time)
- The date of recovery (stop date)
- The time of recovery (stop time)
- The severity of the sign and/or symptom or clinically significant abnormal laboratory value according to NCI-CTC, Version 4.0. If no toxicity grade is described for a given sign, symptom or abnormal laboratory value, the Investigator(s) will grade the severity as mid (grade 1), moderate (grade 2), severe (grade 3), or life-threatening or disabling (grade 4).

- Death (grade 5) as defined by NCI-CTCAE v.4.0 is mainly regarded as an outcome and will be documented accordingly (see below).
- The causal relationship to Avelumab, TACE and radiotherapy as assessed by the Investigator(s); the decisive factor in the documentation is the temporal relation between the AE and the study drug. The following judgments of the causality to study drug or study procedures are to be used:
 - Not Related = not suspected to be reasonably related to the investigational product. AE could not medically (pharmacologically/ clinically) be attributed to the investigational product under study in this protocol
 - Related = suspected to be reasonably related to the investigational product. AE could medically (pharmacologically/ clinically) be attributed to the investigational product under study in this protocol
- Action taken on Avelumab (none, medication discontinued, dose reduction, medication delayed, reduction of infusion rate).
- Other action (none, concomitant medication given, new or prolonged hospitalization, procedural surgery).
- The outcome according to the following definitions:
 - Recovered without sequelae (AE disappeared)
 - Recovered with sequelae (AE has resulted in permanent disability/incapacity)
 - Not yet recovered
 - Not recovered at death
 - Change in toxicity grade/severity or seriousness (e.g., an AE with no change of toxicity grade but newly classified as an SAE due to hospitalization)
 - Fatal (AE resulted in death)
- Concomitant medication given: Yes or No (Note: If this question is answered “Yes” the corresponding serious criteria must be ticked)
 - Subject died
 - Life-threatening
 - New or prolonged hospitalization
 - Persistent/significant disability
 - Congenital abnormality
 - Important medical event
 - Seriousness: Yes or No

If in any one patient the same AE occurs on several occasions, then the AE in question must be documented and assessed anew each time.

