6. STUDY INTERVENTION

6.1 Investigational Product

An investigational product, also known as investigational medicinal product in some regions, is defined as a pharmaceutical form of an active substance or placebo being tested or used as a reference in a clinical study, including products already with a marketing authorization but used for an unauthorized indication, or when used to gain further information about the authorized form.

The investigational product should be stored in a secure area according to local regulations. It is the responsibility of the Investigator(s) to ensure that investigational product is only dispensed to study subjects. The investigational product must be dispensed only from official study sites by authorized personnel according to local regulations.

In this protocol, the investigational products is Avelumab for injection.

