8.3 Early Stopping Rule

Excessive toxicity will be monitored, which includes: (a) grade 4 or 5 hepatic; (b) grade 4 or 5 gastrointestinal; (c) grade 4 thrombocytopenia associated with any bleeding or grade 5 thrombocytopenia; (d) any grade 5 treatment-related adverse event. Assuming no more than a 10% rate of the above AEs on TACE, SBRT, or Avelumab alone, the increase to a rate of 30% or greater in the studied treatment will be considered unacceptable, and the study will be stopped prematurely. Upon the recruitment of these 33 patients, if 14 or more patients had treatment-related SAE, the study will be stopped. The corresponding lower bound of exact one-sided 90% confidence interval is 30.5%. The table below shows the stopping guideline scenarios for the first 8, 16 and 24 patients. For example, the study will be stopped when 11 of the first 24 patients develop an acute toxicity. The upper bound for the confidence intervals is 100%.

| Number of patients with serious adverse event | Number of patients enrolled | Lower bound of exact one-sided 90% confidence interval |
|-----------------------------------------------|-----------------------------|--------------------------------------------------------|
| 5 | 8 | 34.46% |
| 8 | 16 | 31.78% |
| 11 | 24 | 31.48% |

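### Section 7.7.6 asks for causality to avelumab, TACE and radiotherapy but defines Related only against avelumab, and it attaches the serious criteria to the wrong item, so the counts behind Section 8.3 can be misclassified

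*Protocol*

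**What the plan says.** **Causality.** Protocol Section 7.7.6 requires the investigator to record "The causal relationship to Avelumab, TACE and radiotherapy as assessed by the Investigator(s"), and it introduces the two permitted judgments as covering both study drug and study procedures. The judgments themselves are narrower. The positive one reads "Related = suspected to be reasonably related to the investigational product", and Not Related is its mirror image. Section 6.1 states: "In this protocol, the investigational products is Avelumab for injection". The same bullet in 7.7.6 adds that "the decisive factor in the documentation is the temporal relation between the AE and the study drug". Section 7.7.5 asks the investigator "to determine whether an adverse event is considered to be related to the study drug" and lists six factors, of which the first three name the study drug.

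**Seriousness.** In the CRF list of 7.7.6, the note that "the corresponding serious criteria must be ticked" is attached to the yes/no question on concomitant medication. The criteria (death, life-threatening, hospitalization and so on) follow that question. The seriousness yes/no item comes after them, without the note. Section 7.7.2 defines an SAE by the usual outcome criteria and makes no reference to medication.

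**Use.** Section 8.3 says of the 33-patient look: "if 14 or more patients had treatment-related SAE, the study will be stopped". It also lists any grade 5 treatment-related event as excessive toxicity. It sets the 10% reference rate by TACE, SBRT or avelumab alone, and the 30% limit by the studied treatment as a whole.

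**The concern.** The lead-in to the causality bullet requires three attributions, and the definitions support only one. A site that applies the written definition to a liver abscess after TACE (listed in Section 6.3.2), or to radiation-induced liver disease before any infusion (listed in Section 6.4.4), has to answer Not Related. The stopping rule is framed on the combination. Where it depends on relatedness, events from two of the three components can drop out, and the error runs in the unsafe direction: the trial continues when the combination is too toxic. The reported treatment-related toxicity (Section 2.2, objective 4) is exposed in the same way.

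The misplaced note affects the second attribute of a treatment-related SAE. Taken literally, it prompts for serious criteria when an event was medicated and gives no prompt when it was serious.

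**Working it through.** **1. The plan's own bounds.** Section 8.3 gives exact one-sided 90% lower bounds. With x events in n patients, the bound is the 0.10 quantile of a Beta(x, n − x + 1) distribution.

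| Boundary | Section 8.3 | Recomputed |
|---|---|---|
| 5/8 | 34.46% | 34.46% |
| 8/16 | 31.78% | 31.78% |
| 11/24 | 31.48% | 31.48% |
| 14/33 | 30.5% | 30.53% |

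The boundaries are right. The question is what gets counted against them.

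**2. Time before any avelumab.** Inputs: SBRT starts 21–35 days after TACE (Section 6.4), SBRT lasts 5–15 days (6.4.3), and avelumab starts 14–18 days after SBRT (6.5).

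- Shortest: 21 + 5 + 14 = 40 days, or 21 + 4 + 14 = 39 if the first SBRT day is day 0.
- Longest: 35 + 15 + 18 = 68 days, or 35 + 14 + 18 = 67.

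Toxicity from study treatment in these roughly 39–68 days can come only from TACE or SBRT.

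**3. Where relatedness enters Section 8.3.**

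| Part of Section 8.3 | Event named | Relatedness stated? |
|---|---|---|
| Items (a)–(c) | Grade 4–5 hepatic, grade 4–5 gastrointestinal, thrombocytopenia | No |
| Item (d) | Any grade 5 event | Yes |
| Table for 8, 16 and 24 patients | Serious adverse event | No |
| 24-patient example in the text | Acute toxicity | No |
| 33-patient look | SAE | Yes |

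The effect of the causality wording therefore depends on which description is applied at which look. The two extremes are relatedness at the 33-patient look only, and relatedness at all four.

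**4. Chance of stopping.** Exact recursion over the four looks: add the binomial number of new affected patients at each look, remove the paths that reach the boundary, and carry the rest forward.

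| Counted rate | Chance of stopping by 33 patients |
|---|---|
| 20% | 2% |
| 30% | 16% |
| 40% | 54% |
| 45% | 74% |

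**5. Effect of lost events.** The true rate and the share lost are assumptions. If the loss applies at all looks, the counted rate is the true rate times the share kept: 45% × 2/3 = 30%; 40% × 3/4 = 30%; 40% × 1/2 = 20%. If it applies only at 33 patients, the first three looks run at the true rate. At the last look each affected patient is then kept with the stated probability.

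| True rate | Share lost | No loss | Lost at 33-patient look only | Lost at all four looks |
|---|---|---|---|---|
| 45% | one third | 74% | 62% | 16% |
| 40% | one quarter | 54% | 44% | 16% |
| 40% | one half | 54% | 43% | 2% |

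When the loss is confined to the last look it removes almost all of that look's contribution. At a true 45% the first three looks alone already stop the trial with probability 62%.

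**The case against.** The strongest reply is that 7.7.6 does not limit relatedness to avelumab. It names TACE and radiotherapy and says the judgments extend to study procedures, so a careful investigator would attribute a post-TACE abscess to TACE. This is fair. It shows that the bullet contradicts itself, not that it firmly excludes TACE and SBRT events. It does not remove the defect, because the definitions and the decisive-factor sentence still say something else.

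A reader might also infer that the stopping count is bound to be wrong, with the chance of stopping always cut to 16% in the 45% case. The documents do not support that. Items (a)–(c) of Section 8.3 and the table for 8, 16 and 24 patients carry no relatedness condition, so grade 4–5 hepatic toxicity after SBRT counts whatever causality is recorded. The 16% needs relatedness to be applied at every look. It is one end of a range.

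Nor are all six factors in 7.7.5 framed on the study drug. The other three concern the disease, patient risk factors and concomitant medication, and non-treatment causes.

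On seriousness, a reader might infer that medicated post-embolization syndrome (60–80% in Section 6.3.2) would flood the count. That does not follow. Section 7.7.2 still governs what an SAE is, the note asks only for corresponding criteria, and a self-limiting syndrome that is merely medicated meets none. It would also contradict the causality point, under which TACE events leave a treatment-related count. The position of the items suggests that two lines were swapped.

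**Conclusion.** The point holds as a contradiction within the protocol that can misclassify events. The documents do not show that the count will be wrong. The causality part carries the weight: 7.7.6 requires three attributions and defines one, and relatedness is written into the 33-patient look and the grade 5 item of Section 8.3. The seriousness part is a drafting error that conflicts with 7.7.2, and no numerical effect is claimed for it.

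For a one-third loss at a true 45%, the fall in the chance of stopping lies between 12 percentage points (74% to 62%) and 58 (74% to 16%), depending on how Section 8.3 is read. These figures assume the true rate, the share of affected patients whose qualifying events come only from TACE or SBRT, and that all of those are recorded as Not Related. The protocol gives none of these. They also assume complete counts at each look. Wrong as written; a wording correction of moderate severity.

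**What to change.** 1. In 7.7.5 and 7.7.6, define Related and Not Related separately for TACE, SBRT and avelumab, and word the 7.7.5 question and its drug-specific factors to match.
2. Replace the decisive-factor sentence in 7.7.6 with a reference to the 7.7.5 factors.
3. Move the note and the list of serious criteria from the concomitant-medication item to the seriousness item.
4. In 8.3, use one event definition at all four looks. Where it says treatment-related, state that this means related to any of the three components.

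The cost is protocol wording and CRF completion guidance, with no extra patients, visits or tests. The numerical boundaries need not change for this point. The downside is that more events will be counted as related.
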